This is an exploratory study of the energy-intake independent effects of leptin initiation and withdrawal in lipodystrophy. Preliminary data are not available to generate estimates of power for each outcome to be tested. The primary comparisons to be tested for each outcome of interest are results at the end of Period 1 versus the end of Period 2, analyzed separately for each group of subjects (leptin-naïve versus leptin treated). Thus, sample size calculations are based on paired, before and after, comparisons within each group of subjects. The data and references used for power calculations are shown in the table, below. Data in the table using the 10% weight loss model are given as percent change from pre-weight loss values, while data from lipodystrophy patients are given as absolute differences between leptin treated and untreated states. All calculations assumed a sample size of 10 and an alpha of 0.05, without correction for multiple comparisons. Because the standard deviations (SDs) of differences between on and off leptin conditions were not reported in publications, the SDs of the difference (used to calculate power for paired comparisons) was estimated in two ways: First, the SDs of differences are calculated by assuming that the SDs of on and off leptin reported in the literature are independent (Power 1 in the table). Second, a “worst-case scenario” was assumed that the SDs on and off leptin in the literature are perfectly positively correlated (Power 2 in the table). The first scenario is the commonly used method, while the second case is the most conservative calculation.

Outcome	Model	Duration of leptin	Off-leptin mean (SD)	On-leptin mean (SD)	Power 1	Power 2
Total energy expenditure ¹¹ (% Δ in kcal/day)	10% wt loss	5 wk	-22% (15.8)	-6% (4.7)	0.92	0.79
Skeletal muscle work efficiency ¹¹ (% Δ in kcal/min expended during exercise vs. at rest)	10% wt loss	5 wk	20% (12.6)	3% (2.5)	0.99	0.97
Resting energy expenditure ²⁴	lipodystrophy	4 mo	35.5 (8.2)	33.6 (6.7)	0.14	0.11
T3 ¹¹ (% Δ)	10% wt loss	5 wk	-9% (6.3)	3% (3.2)	0.99	0.99

T3 ⁴³ (nmol/L)	lipodystrophy	4 mo	124 (37)	114 (26)	0.18	0.13
T4 ¹¹ (% Δ)	10% wt loss	5 wk	-7% (7.9)	-1% (1.3)	0.77	0.66
fT4 ⁴³ (pmol/L)	lipodystrophy	4 mo	1.05 (0.15)	1.03 (0.15)	0.09	0.08
TSH ⁴³ (μU/mL)	lipodystrophy	4 mo	1.37 (0.37)	1.24 (1.1)	0.10	0.09
Norepinephrine ¹¹ (% Δ)	10% wt loss	5 wk	-12% (15.8)	-7% (12.6)	0.19	0.14
Epinephrine ¹¹ (% Δ)	10% wt loss	5 wk	-40% (35)	28% (47)	0.98	0.83

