Measurements in each of the primary outcomes will be analyzed using the paired t-test (for normally distributed variables) or Wilcoxon paired test (for skewed variables) to test if there is any significant difference between the two study periods (on and off leptin) for each group (leptin naïve and leptin treated), respectively. In addition, mixed models incorporating baseline (pre-diet) parameters as covariates will be used to adjust for any effects of the inpatient, metabolic diet, independent of leptin's effects. For variables with more than 2 measurements during Period 2, repeated measure linear models (Mixed model or GLM) will be used to study the time effect, using pooled data from the 2 periods. Potential covariates to be explored in the model include: Age, sex, race, percent body fat, lean mass, body weight, type of lipodystrophy, and endogenous leptin level. To account for any deviation from the isocaloric protocol diet, actual caloric intake will be included as a covariate in mixed model analyses.

Additional correlations between variables within and between each of the major outcome categories (glucose metabolism, lipid metabolism, and energy expenditure) will be analyzed using either Pearson's correlation or simple linear regressions. These include the following:

1. Association between change in total body insulin sensitivity and changes in hepatic insulin sensitivity, fasting plasma glucose, and C-peptide
2. Association between change in rate of lipolysis, and changes in fasting triglycerides and fatty acid turnover
3. Association between insulin sensitivity and ectopic lipid stores, and rates of lipolysis and fatty acid turnover
4. Association between change in total energy expenditure and changes in resting energy expenditure, skeletal muscle work efficiency, spontaneous physical activity, thyroid function, catecholamines, and cardiac autonomic nervous system tone.

Analysis of Secondary and Exploratory Outcomes

Methods for analysis of secondary outcomes will be similar to those for primary outcomes. In addition, we will perform analysis to study the following associations between categories of outcome measures:

1. Association between the Ectopic Lipid measurements with Glucose and Lipid measurements
2. Association between the Endocrine measurements with Energy Expenditure measurements

Analysis of long-term data

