With the exception of insulin (discussed below) subjects will continue their pre-admission medications throughout the study. This includes oral hypoglycemic agents, lipid-lowering medications, and other medications either related or unrelated to lipodystrophy and its complications.

Glucose Management

Leptin naïve subjects: Leptin naïve subjects who take insulin or insulin secretagogues may be at risk of hypoglycemia after leptin initiation due to improvements in insulin sensitivity. Bedside blood glucose monitoring will be performed prior to meals and at bedtime (or more frequently if clinically indicated) in diabetic

subjects. Adjustments in insulin doses will be made on an as-needed basis to maintain blood glucose within a target range of 100-180 mg/dL.

Leptin treated subjects: Bedside blood glucose monitoring will be performed prior to meals and at bedtime (or more frequently if clinically indicated) in all subjects in this group. In leptin-treated subjects who take insulin, home insulin doses will be continued throughout the study. We anticipate that subjects in the leptin treated group (regardless of whether they require insulin at home) may have worsened insulin sensitivity during leptin withdrawal, and hence, may experience hyperglycemia. As changes in blood glucose are a major outcome of this study, insulin will not be started, nor will home insulin doses be increased, unless a subject has fasting blood glucoses greater than 300 mg/dL, non-fasting glucose > 500, or a 200 mg/dL increase from baseline in either fasting or non-fasting glucose. Unlike patients with type 1 diabetes, patients with lipodystrophy are at extremely low risk of developing diabetic ketoacidosis; hence, the risks associated with short-term hyperglycemia are minimal (see Risks).

Standardized Exercise

In order to maintain physical fitness during the three week hospitalization, sedentary subjects will engage in 30 minutes of walking on a treadmill each day (during both Periods 1 and 2) at a mild to moderate self-selected pace. In subjects who habitually exercise, the duration and intensity of exercise will be increased to be consistent with their typical exercise routine.

Study Procedures

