12. Fasting research blood tests: Fasting glucose, insulin, C-peptide, markers of insulin action (e.g. IGFBP2), lipid panel, free fatty acids, and high-sensitivity C-reactive protein will be measured every other day. Markers of bone turnover (CTX and P1NP) will be obtained twice at the end of Period 1, twice at the end of Period 2, and during the follow-up visit for subjects in the leptin-naïve group. Additional blood samples will be stored for future analysis of leptin and inflammatory markers—as well as used to measure circulating RNA and DNA during periods in which patients do or do not receive leptin, to determine the effects of leptin on circulating nucleic acids and pharmacoepigenomics of leptin therapy.
13. Biochemical evaluation: A baseline biochemical evaluation, which includes: electrolytes, BUN, creatinine, LDH, CPK, SGOT, SGPT, bilirubin, alkaline phosphatase, calcium, magnesium, albumin, protein, iron, and transferrin, will be conducted during Period 1 and at follow-up.
14. Magnetic Resonance Imaging (MRI) and Magnetic Resonance Spectroscopy (MRS): Hepatic, muscle and central body fat will be measured by magnetic resonance imaging (MRI) and magnetic resonance spectroscopy (MRS). MR studies will be performed at the end of Period 1, at the end of Period 2, and during the follow-up visit for subjects in the leptin-naïve group. Studies are performed on a 3T MRI scanner using phased-array coils. B0 shim parameters are optimized with a breath hold B0 mapping method (1). Navigator gated T2 weighted (T2w) and breath-hold T1 weighted (T1w) images in coronal and axial orientations are used to prescribe a 20x20x20 mm³ spectroscopy volume in an area with high signal to noise ratio, free of obvious fatty structures or blood vessels. After additional manual shimming, and optimization of transmit power and WS RF level 32 signals are averaged with a minimum repetition time (TR) of 3s and 35 ms echo time (TE) with WET water suppression (WS) followed by 4 signals averaged with WS RF power set to zero. Spectral data are fitted with AMARES (2) using a model of four resonances for the lipid signals on the WS spectra. Additionally, the apparent T2's of the summed

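### In the leptin treated group, insulin added for high glucose during withdrawal has no place in the analysis, so any such rescue would shrink the measured fasting glucose change

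*Combined protocol and SAP*

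**What the plan says.** For leptin treated subjects, Glucose Management states that "home insulin doses will be continued throughout the study". It expects that subjects "may have worsened insulin sensitivity during leptin withdrawal, and hence, may experience hyperglycemia". It gives a measurement reason for holding insulin back: "As changes in blood glucose are a major outcome of this study". The exceptions follow: "insulin will not be started, nor will home insulin doses be increased, unless a subject has fasting blood glucoses greater than 300 mg/dL". Insulin may also be added when a non-fasting reading passes 500, or when either kind of reading has climbed 200 mg/dL above its starting level.

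Sample Size Justification defines the primary comparison as "results at the end of Period 1 versus the end of Period 2, analyzed separately for each group of subjects". Analysis of Primary Outcomes applies a paired t or Wilcoxon test "to test if there is any significant difference between the two study periods (on and off leptin) for each group", and secondary outcomes are to be handled in a similar way. The candidate covariates are demographic, body composition, lipodystrophy type and endogenous leptin variables. Actual caloric intake is added to account for departures from the diet. Insulin dose and rescue are not mentioned.

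Outcome Measures makes clamp glucose disposal the primary glucose outcome and lipolysis the primary lipid outcome. Fasting glucose, C-peptide and triglycerides are secondary. Under Metabolic Testing, item 12, the fasting glucose, C-peptide and lipid samples "will be measured every other day".

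**The concern.** The event that changes insulin treatment is defined by glucose, and glucose is also an outcome. A subject who passes a limit receives insulin, which lowers later readings. The end-of-Period 2 reading for that subject then reflects withdrawal plus added insulin, but enters the paired test as the off-leptin value. Because withdrawal is expected to raise fasting glucose, the distortion runs toward no effect.

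The plan already adjusts for one departure from constant conditions, caloric intake, but not for this one. If no rule is fixed in advance, the handling will be chosen after it is known which of about 10 subjects were rescued.

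**Working it through.** **1. What happens to a rescued subject.** Withdrawal Criteria lists withdrawn consent, adverse events (with pancreatitis and ketoacidosis as examples), investigator decision and protocol violation. Insulin given under the protocol's own glucose rule is not listed. Nothing in the statistical section excludes, replaces or flags later values. Analysis of the post-rescue value is therefore the default, inferred from silence.

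**2. The plan's own figure.** For fasting glucose the table gives 172 (SD 20) off leptin and 120 (SD 12) on leptin, n = 10, alpha 0.05, with power 1 and 0.99. The difference is 172 − 120 = 52.
- SD of the difference, independent: √(20² + 12²) = 23.3. Two-sided paired t power is 1.000.
- The larger SD of the difference: 20 + 12 = 32. Two-sided paired t power is 0.995.

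The stated figures reproduce.

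**3. How often the fasting triggers would fire on those figures (normal tails).**
- Fasting above 300: (300 − 172)/20 = 6.4 SD, probability about 8 × 10⁻¹¹.
- Rise of 200: (200 − 52)/23.3 = 6.35 SD, probability about 1 × 10⁻¹⁰. With SD 32 it is 4.6 SD, about 2 × 10⁻⁶.
- With all SDs tripled (assumption): 1.6% for the level, and 1.7% for the rise (6.2% at the larger SD of the difference).

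The documents give no data for the non-fasting triggers.

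**4. What a rescue does to the mean change.** Assume that non-rescued subjects rise 52 mg/dL, that a rescued subject would have risen 200, and that insulin holds that rise to R. With k of 10 rescued, the mean without added insulin is [52(10 − k) + 200k]/10 and the analysed mean is [52(10 − k) + Rk]/10.

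| k | Without added insulin | R = 150 | R = 100 | R = 0 |
|---|---|---|---|---|
| 1 | 66.8 | 61.8 (7% less) | 56.8 (15%) | 46.8 (30%) |
| 2 | 81.6 | 71.6 (12%) | 61.6 (25%) | 41.6 (49%) |

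**5. Simulation under wider spread (assumed values).** On- and off-leptin values are independent normals with on-leptin mean 120, table SDs are multiplied as shown, and rescued values are cut to 180.

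| Off-leptin mean | SD multiple | Rescued | Mean change without rescue | Analysed |
|---|---|---|---|---|
| 172 | 1 | about 0% | 52.0 | 52.0 |
| 172 | 2.65 | 1.3% | 52.0 | 50.5 |
| 220 | 2.65 | 8.4% | 99.9 | 88.7 (11% less) |
| 220 | 4 | 20% | 100.0 | 70.6 (29% less) |

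In the last row, two-sided paired t power falls from 0.85 to 0.78.

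**6. Other outcomes.** C-peptide may be affected by added insulin. Lipolysis may be too, but Metabolic Testing item 11 permits an overnight insulin drip before the clamp in insulin-treated subjects, and the test schedule pairs tracer and clamp studies at the end of each Period. Lipolysis may therefore be measured under titrated insulin even without rescue. The clamp runs under its own insulin infusion, so any effect there is indirect and the documents do not show its size or direction.

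**The case against.** The strongest case against is that rescue may hardly occur. The table's fasting figures make it negligible. The one human withdrawal study under constant intake described in the Introduction, a single patient, saw no change in glucose. Leptin treated subjects with HbA1c of 9% or more are excluded, and the Risks text expects the controlled diet to help keep glucose down. This stands as far as it goes: the size cannot be stated as a finding. It does not show that the rate is nil. The table row is a 7-day result from patients with generalized lipodystrophy starting leptin. This trial withdraws leptin for 14 days, admits all subtypes, and also has non-fasting triggers.

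Three stronger readings are tempting and are not supported.
- **A large share of the effect is lost.** With an assumed baseline of 130 (SD 32), true rises of 52, 100 and 150 (SD 60, 80 and 90) and rescued values recorded at 180, the loss is 12%, 36% and 53%. The arithmetic is right, but the documents do not support those rises and spreads as inputs for this trial.
- **Insulin is added only in the largest responders.** That is exact only for the 200 mg/dL rise. The 300 and 500 limits are absolute levels, which a subject with a high baseline can pass after a modest rise.
- **The protocol states that rescued subjects stay in and are analysed.** No sentence says so. Part of Risks/Discomforts was not available in the text reviewed, and that section does hold one withdrawal criterion (elevated lipase) missing from the Withdrawal Criteria list.

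It is also fair to say that the effect of withdrawal including any rescue is a legitimate target. The plan does not name it, and its reason for limiting insulin points to the effect without added insulin.

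**Conclusion.** The concern holds in limited form. The plan has no provision for insulin started or raised during withdrawal, and by default a post-rescue fasting glucose becomes the off-leptin value. Whenever that happens, and the target is the effect without added insulin, the fasting glucose change is biased toward no effect. The clear bias is confined to a secondary outcome in a study that calls itself exploratory. C-peptide and lipolysis may be affected, and the clamp only indirectly.

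The size is unknown because neither the rescue rate nor post-rescue glucose is given. One rescued subject in 10 would cost roughly 7% to 30% of the mean change, if that subject would have risen 200 mg/dL and insulin holds the rise to between 150 and 0. A prespecified rule is worth having because it is cheap and one subject in 10 can matter.

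**What to change.** Leave the clinical rule as it is and change the analysis text only.

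- Record the date and dose of every insulin change in the leptin treated group, and report the number rescued.
- For fasting glucose and C-peptide in this group, prespecify an analysis that uses the last fasting draw before insulin was started or increased. Leave post-rescue draws out of the time-course model for these two outcomes. Report the result beside the end-of-Period 2 comparison.
- For glucose, add a Wilcoxon analysis that gives rescued subjects the worst ranks, as a check.
- For lipolysis, the clamp and triglycerides, keep the end-of-Period 2 value and report the paired result with and without rescued subjects. An early draw should not replace triglycerides: the single withdrawal patient in the Introduction showed a rise only after seven days, so substitution could itself bias toward no effect.

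**Cost.** There is a little more recording and analysis. The pre-rescue value can also fall several days before the end of Period 2, so it reduces the bias without removing it. In the most extreme assumed scenario above (true rise 150), with a linear rise and draws every two days, the median last pre-rescue draw is Day 8. About 25% of the effect is still lost, against 53% with the post-rescue value.

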The primary aim of this study is to determine the energy intake-independent effects of leptin on energy metabolism in lipodystrophic subjects. Important aspects of energy metabolism to be studied include glucose metabolism, lipid metabolism, and energy expenditure. For each of these three aspects of energy metabolism, we will measure a primary, secondary, and one or more exploratory outcomes, as follows:

Glucose Metabolism

- **Primary outcome:** Total body insulin sensitivity (measured as glucose disposal rate during a hyperinsulinemic, euglycemic clamp)
- **Secondary outcomes:**
 - Hepatic insulin sensitivity (measured as suppression of endogenous glucose production during a hyperinsulinemic, euglycemic clamp)
 - Fasting plasma glucose
 - Fasting C-peptide
- **Exploratory outcomes:**
 - Insulin-like growth factor binding protein 2 (IGFBP2) and other novel mediators of leptin action on glycemia

Lipid Metabolism

- **Primary outcome:** Rate of lipolysis (measured using stable isotope tracers)
- **Secondary outcomes:**
 - Fasting plasma triglycerides
- **Exploratory outcomes:**
 - Rate of fatty acid turnover (measured using stable isotope tracers)
 - Liver triglyceride (measured using MRI and MRS)
 - Muscle triglyceride (measured using MRS)

Energy Expenditure

- **Primary outcome:** Total 24 hour energy expenditure (measured using indirect calorimetry in the metabolic chamber)
- **Secondary outcomes:**
 - Resting energy expenditure (measured using indirect calorimetry with a hood)

- Skeletal muscle work efficiency (measured as the exercise-induced incremental change in energy expenditure above resting energy expenditure)
- **Exploratory variables:**
 - Spontaneous physical activity (measure using portable accelerometers)
 - Thyroid function
 - Urine and plasma catecholamines
 - Cardiac autonomic nervous system tone (measured using heart rate variability analysis)

Additional outcomes include the following:

Thermal regulation

- Core versus peripheral body temperature
- Thermal comfort (measured using visual analog scales)

Endocrine

- LH pulsatility analysis

Other

- Blood pressure (measured using 24 hour ambulatory monitoring)
- Hunger and satiety (measured using visual analog scales)
- Markers of bone turnover (β -CTX and P1NP) will be measured to look for potential effects of leptin on bone formation and resorption.

Statistical Considerations

Sample Size Justification

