3. Resting Metabolic Rate (RMR): The RMR will be measured upon awakening before breakfast after a minimum 8 hour fast, in a resting supine position using the standard technique of the Clinical Center. This is done using a microprocessor-controlled indirect calorimetry device (ParvoMedics TrueOne2400, Sandy UT) that measures oxygen consumption and carbon dioxide production. The procedure involves positioning a canopy over the patient's head that allows the patient to exchange gas with an open-circuit design. The recording should be for at least 20 minutes after achieving a steady curve. This measurement is done under conditions of minimal physical activity. The amount of carbon dioxide generated and oxygen consumed by the patient is determined by calorimeter. RMR measurements will be obtained after admission to assist with estimation of caloric requirements, once at the end of Period 1, and approximately every 4 days during Period 2 in order to look for any time-course effects of leptin initiation of withdrawal. RMR will also be measured during the long-term follow-up visit for subjects in the leptin-naïve group
4. DEXA scan for total body composition: Measurements of fat-free mass will be obtained and used to normalize energy expenditure measurements. Measurements will be obtained at the end of Period 1 and the end of Period 2, and during the long-term follow-up visit for subjects in the leptin-naïve group, immediately after leaving the metabolic chamber. A DEXA scan (iDXA, GE Healthcare, Madison WI) will be performed to determine total and regional body fat and lean soft tissue masses, bone mineral content and density. DEXA produces photons at two different energy levels, 40 and 70 KeV. The photons pass through tissues and attenuate at rates related to elemental composition. Bone mineral, with highly attenuating calcium and phosphorous, is readily distinguished from soft tissues. The different elemental profiles of fat and bone-mineral free lean components allows for the analysis of soft tissue fat content, so that bone mineral, fat, and bone mineral fat-free lean components may be resolved.
5. Blood pressure monitoring: Blood pressure will be monitored every 30 minutes using an automated ambulatory blood pressure monitor. Because leptin's effects on blood pressure have been reported to be rapid and transient following leptin initiation ([name], unpublished observations), testing will be

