focused on the 48 hours immediately before and after leptin initiation and withdrawal. An additional 48 hours of monitoring will be performed at the end of Period 2, and during the long-term follow-up visit for subjects in the leptin-naïve group, to look for longer term effects.

6. Heart rate variability: Heart rate will be measured and recorded using a portable ECG Holter monitor, which will be downloaded and analyzed for heart-rate variability using power spectrum analyses. Testing will be performed in conjunction with blood pressure monitoring.
7. Visual Analog Scales (hunger, thermal regulation): Patients will be given a questionnaire to determine their level of thermal comfort and hunger using visual analog scales (VAS), as shown in Appendix III. The hunger VAS question has been characterized previously, and is digitized exactly onto an iPad app⁴⁴. Testing does not require supervision, and will be performed on a daily basis after lunch.
8. Skin temperature: Wireless probes (iButtons, Maxim Inc., Sunnyvale, CA) will record skin temperature with data reported each minute. The positions of the skin sensors at five sites (deltoid, hand, pectoralis major, anterior thigh, and shin) will be according to the ISO standards⁴⁵. Skin temperature monitoring will be performed prior to, during, and for one hour following each exercise test, as well as throughout each stay in the metabolic chamber.

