Appendix A: Sample Patient Calendars

Long-term follow-up (leptin naïve subjects, only)

Study Day	0	1	2	3	4	5
Time						
5:00						
6:00		Fasting labs	LH sampling			
6:30						
7:00		OGTT (NPO)	REE		Start 24 hr urine	Stop 24 hr urine
7:30					Start skin temp	DEXA
8:00					Chamber	
8:30						Stop skin temp
9:00			Start Actigraph			Stop Actigraph
9:30			Skin temp monitor	Clamp		
10:00			Exercise test			
10:30						Discharge
11:00			Skin temp monitor			
12:00						
13:00	Admit					
14:00						
15:00						
16:00						
17:00			Start HR monitor	Stop HR monitor		
18:00				Start BP monitor	Stop BP monitor	
19:00						
20:00						
23:00		8 hr LH sampling				

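### The sample follow-up calendar schedules two separate 24-hour heart rate and blood pressure recordings where the protocol text calls for one shared 48-hour recording

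*Combined protocol and SAP*

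**What the plan says.** Metabolic Testing, item 5, sets the method: "Blood pressure will be monitored every 30 minutes using an automated ambulatory blood pressure monitor". In the short-term stay the monitoring is "focused on the 48 hours immediately before and after leptin initiation and withdrawal". The item then continues: "An additional 48 hours of monitoring will be performed at the end of Period 2, and during the long-term follow-up visit", the latter for the leptin-naïve group. Item 6 (heart rate variability, by Holter monitor) adds: "Testing will be performed in conjunction with blood pressure monitoring".

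The test schedule under Study Procedures agrees. It ticks blood pressure and heart rate on the same days: -2, -1, 0, 1, 11 and 12. The section on long-term follow-up says testing at that visit is to repeat what was done in Period 1. Analysis of long-term data plans paired comparisons of follow-up with baseline.

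Two other places differ. Outcome Measures describes the outcome as "Blood pressure (measured using 24 hour ambulatory monitoring". In Appendix A, the sample long-term follow-up calendar places "Start HR monitor" on Day 2 and "Stop HR monitor" on Day 3, both at 17:00. It places "Start BP monitor" on Day 3 at 18:00, with the matching stop on Day 4 at 18:00.

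**The concern.** A paired change from baseline is interpretable when the two recordings are made under the same conditions. The Period 1 recording covers the clamp day and the chamber day for both signals. On the calendar's timing, each follow-up signal has half that duration and sees only one of the two procedures, and not the same one.

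The two days differ by design. One has an insulin and dextrose infusion with blood sampling every 5 minutes; the other has confinement in the calorimeter with a treadmill walk. Part of any long-term change in blood pressure or heart rate variability could therefore reflect what the subject was doing while recorded.

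Two further consequences follow. Heart rate and blood pressure could not be related to each other within the same hours at follow-up. The plan also relates change in total energy expenditure to change in cardiac autonomic tone and carries similar methods to the long-term data, but the follow-up Holter would miss the chamber stay in which energy expenditure is measured.

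**Working it through.** No power or sample-size figure is involved. The check is on clock times.

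**Inputs.** Follow-up calendar: heart rate Day 2 17:00 to Day 3 17:00; blood pressure Day 3 18:00 to Day 4 18:00; clamp Day 3 9:30; chamber from Day 4 8:00. Test schedule: clamp on Days -2 and 11, chamber on Days -1, 6 and 12. Dosing of metreleptin: first dose in naïve subjects at about 8 am on Day 0, so the 48 hours before it run from about Day -2 8:00 to Day 0 8:00. DEXA is on Day 0, directly after the chamber.

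**The 48-hour figure in the short-term stay.** There are two ticked days before leptin starts (-2, -1), two after (0, 1) and two at the end of Period 2 (11, 12), identical for both signals. The stated 48 hours reproduces, and the first and last pairs each hold one clamp day and one chamber day.

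**The 48-hour figure at follow-up.** It does not reproduce.
- Heart rate: Day 3 17:00 minus Day 2 17:00 = 24 h.
- Blood pressure: Day 4 18:00 minus Day 3 18:00 = 24 h.
- Overlap: 0 h. Blood pressure starts 18:00 − 17:00 = 1 h after heart rate stops.
- Scheduled blood pressure readings at one per 30 minutes: 24 × 2 = 48, against 48 × 2 = 96.

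**Content of each window** (taking the Period 1 chamber stay as about Day -1 8:00 to Day 0 8:00, an assumption, since the short-term calendar as available shows no chamber times):

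| Recording | Length | Clamp | Chamber hours |
|---|---|---|---|
| Period 1, both signals | 48 h | yes | about 24 (24/48 = 50%) |
| Follow-up heart rate | 24 h | yes | 0 (0%) |
| Follow-up blood pressure | 24 h | no | 18:00 − 8:00 = 10 (10/24 = 42%) |

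**Nights.** Period 1 covers the night between clamp and chamber and the chamber night. Follow-up blood pressure covers the first of these. Follow-up heart rate covers only the night before the clamp, which falls before the Period 1 recording begins. On that night insulin-treated subjects may be on an insulin drip. If the tracer study is run with the clamp, as in Period 1, deuterated water is also given then.

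**Can Period 1 be trimmed to match?**
- Blood pressure: the clock-matched window is about Day -2 18:00 to Day -1 18:00. It lies wholly inside the Period 1 recording and, on the assumption above, also holds 10 chamber hours.
- Heart rate: the matched window would be Day -3 17:00 to Day -2 17:00. Recording starts on Day -2, at about 8:00, so only 17:00 − 8:00 = 9 of 24 h would exist.

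**The case against.** The strongest reply is that the calendar is only a sample, that the protocol lets test times shift a little for practical reasons, and that the text already states the intent: 48 hours, both signals together, repeating Period 1. This stands to the extent that the mismatch does harm only if the visit is run as the calendar shows. But halving the duration and removing all overlap is more than a small shift in timing.

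A second reply is that the table may have been damaged in conversion from PDF. The short-term calendar in the same appendix has lost most of its entries, and the follow-up calendar shows no MRI or tracer study although both are planned at that visit. Damage cannot be excluded. The clamp, chamber, urine and DEXA entries do fall in a sensible order, however, and each of the four monitor entries sits in a complete row.

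A third reply is that the 24-hour wording in Outcome Measures merely names the technique. That is a fair reading, but it still leaves open which 24 baseline hours would be paired with follow-up.

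A reader might also infer that blood pressure moves from half chamber day to all chamber day, and heart rate from half to all clamp day, so that the bias is half the difference between the two days. The documents do not support this. The chamber share of the blood pressure window falls slightly, from about 50% to 42%. The heart rate window opens 16.5 hours before the clamp entry. The plan does not say that either endpoint is a simple mean over the recording, and it gives no between-day difference, so any figure in mmHg would be invented.

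**Conclusion.** The point holds as an internal contradiction with a minor analytic consequence. The text and the test schedule give one shared 48-hour recording; the sample follow-up calendar gives 24 hours per signal with none in common. If the calendar is followed, the paired long-term comparison uses recordings that differ in duration and activity content, and no simultaneous heart rate and blood pressure data exist at follow-up. The size and direction of any resulting bias cannot be derived from the documents.

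This rests on the calendar cells having been read in their true columns and on visits having followed them. It should not be taken to show that every leptin-naïve subject's long-term result is affected.

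The stakes are low. Blood pressure is an additional outcome and heart rate variability is exploratory. The protocol itself says the long-term data cannot address effects independent of energy intake. The Period 1 versus Period 2 comparison is unaffected, because its recordings match.

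**What to change.** Correct the follow-up calendar to one concurrent 48-hour blood pressure and heart rate recording spanning the clamp and chamber days, as Metabolic Testing items 5 and 6 state. For example, it could start on the morning of Day 3 before the clamp and end on the morning of Day 5 as the subject leaves the chamber, ahead of the 10:30 discharge. This adds 24 hours of wear per device within the same admission. State in Outcome Measures whether 24 hours is the summary period or only the name of the method.

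For visits already run to the calendar, add two rules to Analysis of long-term data:
- Compare follow-up blood pressure with the clock-matched Period 1 window, about Day -2 18:00 to Day -1 18:00. This needs no new data, provided the Period 1 recordings are time-stamped.
- Limit the heart rate variability comparison to clock hours and activities present in both recordings. Only about 9 daytime hours on the clamp day are likely to qualify, so this is a partial repair and should be reported as such. A full trim of Period 1 is not available for this signal.
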